### **Definitions**

#### **Potential Hy's Law (PHL)**

Aspartate Aminotransferase (AST) or Alanine Aminotransferase (ALT)  $\geq 3x$  Upper Limit of Normal (ULN) **and** Total Bilirubin (TBL)  $\geq 2x$ ULN at any point during the study irrespective of an increase in Alkaline Phosphatase (ALP). The elevations do not have to occur at the same time or within a specified time frame.

#### **Hy's Law (HL)**

AST or ALT  $\geq 3x$  ULN **and** TBL  $\geq 2x$ ULN, where no other reason, other than the IMP, can be found to explain the combination of increases, e.g., elevated ALP indicating cholestasis, viral hepatitis, another drug. The elevations do not have to occur at the same time or within a specified time frame.

#### **Identification of potential hy's law cases**

In order to identify cases of PHL it is important to perform a comprehensive review of laboratory data for any patient who meets any of the following identification criteria in isolation or in combination:

- ALT  $\geq 3x$ ULN
- AST  $\geq 3x$ ULN
- TBL  $\geq 2x$ ULN

When a patient meets any of the identification criteria, in isolation or in combination, the central laboratory will immediately send an alert to the Investigator (also sent to AstraZeneca representative).

The Investigator will also remain vigilant for any local laboratory reports where the identification criteria are met, where this is the case the Investigator will:

- Request a repeat of the test (new blood draw) by the central laboratory
- Complete the appropriate unscheduled laboratory CRF module(s) with the original local laboratory test result

When the identification criteria are met from central or local laboratory results the Investigator will without delay:

- Determine whether the patient meets PHL criteria (see [Definitions](#) of this Appendix for definition) by reviewing laboratory reports from all previous visits (including both central and local laboratory results)

### **Follow-up**

#### **Potential Hy's Law criteria not met**

If the patient does not meet PHL criteria the Investigator will:

- Inform the AstraZeneca representative that the patient has not met PHL criteria.
- Perform follow-up on subsequent laboratory results according to the guidance provided in the Clinical Study Protocol.

#### **Potential Hy's Law criteria met**

If the patient does meet PHL criteria the Investigator will:

- Notify the AstraZeneca representative who will then inform the central Study Team

The Study Physician contacts the Investigator, to provide guidance, discuss and agree an approach for the study patients' follow-up and the continuous review of data. Subsequent to this contact the Investigator will:

- Monitor the patient until liver biochemistry parameters and appropriate clinical symptoms and signs return to normal or baseline levels, or as long as medically indicated
- Investigate the etiology of the event and perform diagnostic investigations as discussed with the Study Physician
- Complete the three Liver CRF Modules as information becomes available

- If at any time (in consultation with the Study Physician) the PHL case meets serious criteria, report it as an SAE using standard reporting procedures

### **Review and Assessment of potential Hy's law cases**

The instructions in this Section should be followed for all cases where PHL criteria are met.

No later than 3 weeks after the biochemistry abnormality was initially detected, the Study Physician contacts the Investigator in order to review available data and agree on whether there is an alternative explanation for meeting PHL criteria other than DILI caused by the IMP. The AstraZeneca Medical Science Director and Global Safety Physician will also be involved in this review together with other patient matter experts as appropriate.

According to the outcome of the review and assessment, the Investigator will follow the instructions below.

If there **is** an agreed alternative explanation for the ALT or AST and TBL elevations, a determination of whether the alternative explanation is an AE will be made and subsequently whether the AE meets the criteria for a SAE:

- If the alternative explanation is **not** an AE, record the alternative explanation on the appropriate CRF
- If the alternative explanation is an AE/SAE, record the AE /SAE in the CRF accordingly and follow the AZ standard processes

If it is agreed that there is **no** explanation that would explain the ALT or AST and TBL elevations other than the IMP:

- Report an SAE (report term 'Hy's Law') according to AstraZeneca standard processes.
- The 'Medically Important' serious criterion should be used if no other serious criteria apply
- As there is no alternative explanation for the HL case, a causality assessment of 'related' should be assigned.

If, there is an unavoidable delay, of over 3 weeks, in obtaining the information necessary to assess whether or not the case meets the criteria for HL, then it is assumed that there is no alternative explanation until such time as an informed decision can be made:

- Report an SAE (report term 'Potential Hy's Law') applying serious criteria and causality assessment as per above

- Continue follow-up and review according to agreed plan. Once the necessary supplementary information is obtained, repeat the review and assessment to determine whether HL criteria are met. Update the SAE report according to the outcome of the review

### **Actions required when potential Hy's law criteria are met before and after starting study treatment**

This section is applicable to patients who meet PHL criteria on study treatment having previously met PHL criteria at a study visit prior to starting study treatment.

At the first on study treatment occurrence of PHL criteria being, even if there has been no significant change the patient's condition compared with pre-study treatment visits, the Investigator will:

- Notify the AstraZeneca representative who will inform the central Study Team.
- Follow the subsequent process described is [Potential Hy's Law criteria met](#) of this Appendix.

### **Actions required for repeat episodes of potential hy's law**

This section is applicable when a patient meets PHL criteria on study treatment and has already met PHL criteria at a previous on study treatment visit.

The requirement to conduct follow-up, review and assessment of a repeat occurrence(s) of PHL is based on the nature of the alternative cause identified for the previous occurrence.

The Investigator should determine the cause for the previous occurrence of PHL criteria being met and answer the following question:

- Was the alternative cause for the previous occurrence of PHL criteria being met chronic or progressing malignant disease or did the patient meet PHL criteria prior to starting study treatment and at their first on study treatment visit as described in [Actions required when potential Hy's law criteria are met before and after starting study treatment](#)?

If No: follow the process described in [Potential Hy's Law criteria met](#) of this Appendix

---

 A 'significant' change in the patient's condition refers to a clinically relevant change in any of the individual liver biochemistry parameters (ALT, AST or total bilirubin) in isolation or in combination, or a clinically relevant change in associated symptoms. The determination of whether there has been a significant change will be at the discretion of the Investigator; this may be in consultation with the Study Physician if there is any uncertainty.

If Yes:

Determine if there has been a significant change in the patient's condition#3 compared with when PHL criteria were previously met

- If there is no significant change no action is required
- If there is a significant change follow the process described in [Potential Hy's Law criteria met](#) of this Appendix

---

 A 'significant' change in the patient's condition refers to a clinically relevant change in any of the individual liver biochemistry parameters (ALT, AST or total bilirubin) in isolation or in combination, or a clinically relevant change in associated symptoms. The determination of whether there has been a significant change will be at the discretion of the Investigator; this may be in consultation with the Study Physician if there is any uncertainty.

## Appendix D Anaphylaxis: definition, signs, symptoms and management

### Introduction

As with any antibody, allergic reactions to dose administration are possible. The World Health Organization (WHO) has categorized anaphylaxis into 2 subgroups, which are clinically indistinguishable: immunologic [IgE-mediated and non-IgE-mediated (e.g., IgG and immune complex mediated) and nonimmunologic (Kemp et al 2008)]. The clinical criteria for defining anaphylaxis for this study are listed in [Clinical Criteria for Defining Anaphylaxis and Immune Complex Disease](#). A guide to the signs and symptoms and management of acute anaphylaxis is provided in [Signs and Symptoms and Management of Acute Anaphylaxis](#).

Appropriate drugs, such as epinephrine, antihistamines, corticosteroids, etc, and medical equipment to treat anaphylactic reactions should be available at study sites, and study personnel should be trained to recognise and treat anaphylaxis according to local guidelines.

If an anaphylactic reaction occurs, a blood sample should be drawn from the patient as soon as possible after the event, at 90 minutes $\pm$ 30 minutes after the event, and at discharge for analysis of serum tryptase at a local laboratory. Other blood testing relevant to the diagnosis of anaphylaxis may be obtained at a local lab at the discretion of the Investigator.

### Clinical Criteria for Defining Anaphylaxis and Immune Complex Disease

#### Anaphylaxis

In adults, anaphylaxis is highly likely when any one of the following 3 criteria is fulfilled:

1. Acute onset of an illness (minutes to several hours) with involvement of the skin, mucosal tissue, or both (e.g., generalized hives, pruritus or flushing, swollen lips-tongue-uvula)

AND AT LEAST ONE OF THE FOLLOWING:

- (a) Respiratory compromise (e.g., dyspnea, wheeze-bronchospasm, stridor, reduced PEF, hypoxemia).
  - (b) Reduced blood pressure (BP) or associated symptoms of end-organ dysfunction (eg, hypotonia [collapse], syncope, incontinence).
2. Two or more of the following that occur rapidly after exposure to a **likely** allergen for that patient (minutes to several hours):
    - (a) Involvement of the skin-mucosal tissue (e.g., generalized hives, itch-flush, swollen lips-tongue-uvula).
    - (b) Respiratory compromise (e.g., dyspnea, wheeze-bronchospasm, stridor, reduced PEF, hypoxemia).

- (c) Reduced BP or associated symptoms (e.g., hypotonia [collapse], syncope, incontinence).
  - (d) Persistent gastrointestinal symptoms (e.g., crampy abdominal pain, vomiting).
3. Reduced BP after exposure to known allergen for that patient (minutes to several hours): Adults: systolic BP of less than 90 mm Hg or greater than 30% decrease from that patient's baseline.

### **Immune Complex Disease**

Immune complex disease or Hypersensitivity Type III is evoked by the deposition of antigen-antibody or antigen-antibody-complement complexes on cell surfaces, with subsequent involvement of breakdown products of complement, platelets, and polymorphonuclear leukocytes, and development of vasculitis; serum sickness and nephritis is common.

### **Signs and Symptoms and Management of Acute Anaphylaxis**

Anaphylaxis is an acute and potentially lethal multi-system allergic reaction in which some or all of the following signs and symptoms occur:

- Diffuse erythema
- Pruritus
- Urticaria and/or angioedema
- Bronchospasm
- Laryngeal edema
- Hypotension
- Cardiac arrhythmias
- Feeling of impending doom
- Unconsciousness
- Shock

Other earlier or concomitant signs and symptoms can include:

- Itchy nose, eyes, pharynx, genitalia, palms, and soles
- Rhinorrhea
- Change in voice
- Metallic taste
- Nausea, vomiting, diarrhea, abdominal cramps and bloating
- Lightheadedness
- Headache
- Uterine cramps
- Generalized warmth

## **Management of Acute Anaphylaxis**

### **Immediate intervention**

1. Assessment of airway, breathing, circulation, and adequacy of mentation
2. Administer epinephrine intramuscularly every 5-15 minutes, in appropriate doses, as necessary, depending on the presenting signs and symptoms of anaphylaxis, to control signs and symptoms and prevent progression to more severe symptoms such as respiratory distress, hypotension, shock and unconsciousness.

### **Possibly appropriate, subsequent measures depending on response to epinephrine**

1. Place patient in recumbent position and elevate lower extremities.
2. Establish and maintain airway.
3. Administer oxygen.
4. Establish venous access.
5. Normal saline IV for fluid replacement.

### **Specific measures to consider after epinephrine injections, where appropriate**

1. Consider epinephrine infusion.
2. Consider H1 and H2 antihistamines.
3. Consider nebulized  $\beta$ 2 agonist [e.g., albuterol (salbutamol)] for bronchospasm resistant to epinephrine.
4. Consider systemic corticosteroids.
5. Consider vasopressor (e.g. dopamine).
6. Consider glucagon for patient taking b-blocker.
7. Consider atropine for symptomatic bradycardia.
8. Consider transportation to an emergency department or an intensive care facility.
9. For cardiopulmonary arrest during anaphylaxis, high-dose epinephrine and prolonged resuscitation efforts are encouraged, if necessary.

## Appendix E Background Therapy Equivalence Table

### Estimated daily dosage for inhaled corticosteroids

Asthma Therapy Inhaled Corticosteroid	Total Daily Dose (µg/day)	
	Medium	High
Beclomethasone dipropionate (CFC)	>500 - 1000	>1000 - 2000
Beclomethasone dipropionate (HFA)	>240 - 480	>480
Beclomethasone dipropionate (Fostair)	>200 - 400	>400 - 800
Budesonide	>400 to 800	>800 - 1600
Budesonide, if as delivered dose (e.g. Symbicort)	>320 to <640	≥640 - 1280
Ciclesonide	>160 - 320	>320 - 1280
Flunisolide	>1000 - 2000	>2000
Fluticasone propionate (DPI)	>250 - 500	>500 - 1000
Fluticasone propionate (HFA)	>250 - 500	>500
Fluticasone furoate (DPI)	NA	200
Mometasone furoate	>220-440	>440
Triamcinolone acetonide	>1000 - 2000	>2000

Note: Categories of “medium” and “high” doses are based on published information and available studies (at the time of GINA 2018 publication), including direct comparisons where available. Doses may be country-specific depending on labelling requirements. For new preparations, manufacturer’s information should be reviewed carefully; products containing the same molecule may not be clinical equivalent (GINA 2018).

## Appendix F Restricted and prohibited medications

### Asthma medication restrictions

**Table 5 Asthma medication restrictions**

Medication	Prohibited/ restricted	Details
Maintenance of asthma controller medications (ICS-LABA)	Restricted	
Changes in dose and regimen should not be done from visit 1 and throughout the study (unless there is a medical need as judged by the Investigator and discussed beforehand with AstraZeneca Study Physician)
 
Usual ICS-LABA should not be taken prior to scheduled spirometry, ECG and home PEF assessments (to be administered once assessments are completed)

Short acting beta2-agonists (SABA)	Restricted	
Regular scheduled use in the absence of any asthma symptoms and/or planned exercise is discouraged from Visit 1 throughout the study.
 
Rescue use of SABA administered via nebulisation is allowed.
 
SABA should not be used within 6 hours prior to scheduled spirometry, ECG and home lung function assessments.

Additional Maintenance Controllers (e.g. LTRAs, tiotropium, cromone, theophylline and oral corticosteroids)	Restricted	
Have been used for at least 1 month prior to Visit 1; stable dose during the treatment period.
 
Usual controller should not be taken prior to scheduled spirometry, ECG and home PEF assessments (to be administered once assessments are completed).

Short acting anticholinergics (e.g. ipratropium)	Restricted	
Not allowed from Visit 1 and throughout the study as a rescue treatment for worsening asthma symptoms outside of managing an asthma exacerbation event.
 
May be used for managing an asthma exacerbation event.

Long-acting beta-agonists as a reliever (e.g. Symbicort)	Prohibited	
Not allowed from Visit 1 and throughout the study duration

Maintenance and Reliever Treatment)		
Five- lipoxygenase inhibitors (e.g. Zileuton)	Prohibited	Not allowed 30 days prior to Visit 1; during treatment period

**Other medication restrictions. Usage of the following restricted medications might be acceptable for AE treatment after discussion with AstraZeneca Study Physician.**

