### **3.8 Restrictions**

#### **3.8.1 Asthma medication restrictions**

##### **(a) Use of short-acting $\beta_2$ agonists (SABA)**

Regularly scheduled SABA use in the absence of any asthma symptoms and/or planned exercise is discouraged from enrolment and throughout the study duration.

Prophylactic use of SABA in the absence of symptoms (e.g., prior to planned exercise) is discouraged. However, if deemed necessary by the patient and Investigator, it can be used, but prophylactic inhalations should not be recorded in the Asthma Daily Diary, such use should be documented in medical notes and recorded in the Electronic Case Report Form (eCRF).

SABA via a metered dose device is permitted as needed for worsening asthma symptoms (ie, rescue use) and will be recorded in the Asthma Daily Diary as number of inhalations.

Rescue use of SABA administered via jet or ultrasonic nebulisation is allowed. Occasions where SABA was administered via nebulisation will be recorded separately from metered dose inhaler (MDI) inhalations in the Asthma Daily Diary.

**(b) Use of short acting anticholinergics** (e.g., ipratropium) as a rescue treatment for worsening asthma symptoms outside of managing an asthma exacerbation event is not allowed from enrolment and throughout the study duration

**(c) Use of long-acting beta-agonists as a reliever** (e.g., Symbicort Maintenance and Reliever Treatment) is not allowed from enrolment and throughout the study duration

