**(f) Asthma medication restrictions prior to home peak expiratory flow testing**

Patients should avoid taking their morning asthma controllers prior to the morning home Peak Expiratory Flow (PEF) testing, and should conduct the evening home PEF testing before taking evening asthma controllers. When possible, home PEF testing, should be taken at least 6 hours after the last dose of SABA rescue medication.

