## **5. STUDY ASSESSMENTS AND PROCEDURES**

### **5.1 Efficacy assessments**

#### **5.1.1 Assessment of asthma exacerbations**

For the purpose of the protocol, an asthma exacerbation will be defined as a worsening of asthma that leads to any of the following:

- Use of systemic corticosteroids (or a temporary increase in a stable oral corticosteroid background dose) for at least 3 days; a single depo-injectable dose of corticosteroids will be considered equivalent to a 3-day course of systemic corticosteroids
- An emergency room/urgent care visit (defined as evaluation and treatment for <24 hours in an emergency department or urgent care centre) due to asthma that required systemic corticosteroids for at least 3 days (as per above)
- An inpatient hospitalization (defined as admission to an inpatient facility and/or evaluation and treatment in a healthcare facility for  $\geq 24$  hours) due to asthma

Worsening of asthma is defined as new or increased symptoms and/or signs (examination or lung function) that can be either concerning to the patient (patient-driven) or related to an Asthma Daily Diary alert (diary-driven). The ePRO device will be programmed to alert both the patient and study centre when certain pre-specified worsening thresholds are crossed including:

- Decrease in morning peak flow  $\geq 30\%$  on at least 2 of 3 successive days compared with baseline (last 10 days of run-in), and/or
- A  $\geq 50\%$  increase in rescue medication on at least 2 of 3 successive days compared with the average use for the previous week, and/or use of 1 new or additional nebulized  $\beta_2$  agonist on at least 2 of 3 successive days compared with the average use for the previous week, and/or
- Nocturnal awakening due to asthma requiring rescue medication use for at least 2 of 3 successive nights, and/or
- An increase in total asthma symptom score (the sum of day time [evening assessment] and night time [morning assessment] of at least 2 units above the run-in average (last 10 days of run-in), or the highest possible score (daily score of 6), on at least 2 of 3 successive days

If an exacerbation event is not associated with deterioration in at least 1 of the pre-specified objective measurements, the Investigator will have to justify the decision for defining the event as an exacerbation and record it in the eCRF. Events that are not supported by any objective assessment will be deemed not to be a protocol-defined exacerbation.

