### **5.1.3 Home peak expiratory flow testing**

An electronic, hand-held spirometer (peak flow meter) will be dispensed to the patient on Visit 2 (after respiratory inclusion criteria have been confirmed, see Section 3.1, criterion 8 and 11).

Home peak expiratory flow (PEF) testing will be performed by the patient in the morning upon awakening (and prior to taking their AM asthma controller) and in the evening at bedtime (and prior to taking their PM asthma controller). Recording of home peak expiratory flow should start from the evening of Visit 2 until the morning of Visit 17 using an ePRO device. When possible, ambulatory lung function measurements should be taken at least 6 hours after the last dose of SABA rescue medication.

Patients should perform 3 successive peak flow manoeuvres while sitting or standing, but in the same position at every testing; the highest of the 3 values will be captured for the morning and for the evening manoeuvres.

Investigator/authorized delegate will check patient's adherence to correct use of the peak flow meter at each clinic visit as shown in Table 2 (or on IPD Visit if prematurely discontinued from the study).

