### **Rescue medication**

The number of rescue medication inhalations and nebulizer treatments taken will be recorded by the patient in the Asthma Daily Diary twice daily. The number taken between the morning and evening lung function assessments will be recorded in the evening. The number of inhalations taken between the evening and morning lung function assessments will be recorded in the morning. Rescue medication usage is captured in the daily diary as the number of inhaler puffs and the number of times a nebulizer is used. Rescue medication usage will be summarized as the number of puffs with 1 instance of nebulizer use converted to 2 puffs.

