### **7.6.1.2 Rescue medication**

Salbutamol, or albuterol, or levalbuterol may be used as rescue medication during the study in the event of a worsening of asthma symptoms. Patients, who are already on nebulized SABA as rescue medication, can continue their use throughout the study.

As with background ICS-LABA medication, rescue medication is not regarded as an IP, but will be provided by or reimbursed to AstraZeneca according to local regulations, in order to ensure access to essential rescue therapy.

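### Minor, wrong as written: the SABA row of Table 5 extends the clinic 6-hour rule, without qualification, to the twice-daily home lung function tests, against Sections 3.8.1(f) and 5.1.3

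*Supplement*

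**What the plan says.** Appendix F, Table 5, SABA row: "SABA should not be used within 6 hours prior to scheduled spirometry, ECG and home lung function assessments". The same cell discourages regular scheduled use in the absence of symptoms or planned exercise, and adds: "Rescue use of SABA administered via nebulisation is allowed".

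The body of the protocol handles the three kinds of assessment separately:

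- **Clinic spirometry, Section 3.8.1(e):** no SABA in the 6 hours beforehand, without qualification.
- **ECG, Section 3.8.1(h):** SABA to be avoided in the 6 hours beforehand.
- **Home PEF, Section 3.8.1(f):** "When possible, home PEF testing, should be taken at least 6 hours after the last dose of SABA rescue medication".
- **Home PEF, Section 5.1.3:** "When possible, ambulatory lung function measurements should be taken at least 6 hours after the last dose of SABA rescue medication".

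On rescue use, Section 3.8.1(a) says "SABA via a metered dose device is permitted as needed for worsening asthma symptoms", and Section 7.6.1.2 says that salbutamol, albuterol or levalbuterol "may be used as rescue medication during the study in the event of a worsening of asthma symptoms". Neither section sets a time-of-day limit.

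**The concern.** Table 5 merges three rules into one, and the merger changes the home rule in two ways. The feasibility qualifier is lost. The object of the rule also shifts: the body times the test around the drug, whereas the table restricts the drug around the test.

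For an occasional clinic visit a 6-hour restriction is manageable. Home PEF is measured twice every day from the evening of Visit 2 to the morning of Visit 17, in patients enrolled because their asthma is uncontrolled and prone to exacerbation. Staff who worked from the table alone could advise against the main reliever for much of each day, including the hours before the waking test. Section 3.8.2 directs readers to Appendix F for the medication restrictions, so it is a natural quick reference at site.

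**Working it through.** The plan gives no figure to reproduce. The check is a comparison of texts, followed by a short calculation of how far the table's wording reaches.

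**1. Does one act get two answers?** Take a patient who needs rescue SABA 2 hours before a home test and cannot sensibly delay the test.

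- Under 3.8.1(f) and 5.1.3 this is compliant, because the 6-hour gap applies only where feasible.
- Under 3.8.1(a) and 7.6.1.2 the dose itself is permitted.
- Under Table 5 it is a departure, because the dose falls within 6 hours before a home lung function test.

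**2. Does the table's sentence reach rescue doses?** It says SABA without limit. For clinic spirometry, Section 3.8.1(e) sets out what to do when rescue SABA was taken within 6 hours, and Section 5.1.2 applies the 6-hour limit to rescue SABA by name. The protocol's 6-hour rule therefore includes rescue use.

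**3. Which text states the intended rule?** Other operative text takes rescue between the evening and morning tests for granted:

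- Section 5.1.1, diary alert: "Nocturnal awakening due to asthma requiring rescue medication use for at least 2 of 3 successive nights".
- Section 5.3.2.1, diary: "The number of inhalations taken between the evening and morning lung function assessments will be recorded in the morning".
- Section 8.5.2.1 has a secondary endpoint based on nights with awakening that require rescue.
- Inclusion criterion 10 counts days of rescue SABA use.

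Table 5 is the outlier.

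**4. How far does the literal wording reach?** Inputs: two home tests a day, on waking and at bedtime (Section 5.1.3); a 6-hour window before each (Table 5); an evening-to-morning interval of L hours. The documents do not give L, so it is assumed, with a range of 4 to 10.

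Hours covered per day = 6 + 6 − overlap, where overlap = max(0, 6 − L).

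Share of the night interval covered = min(6, L) / L.

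| L (h) | Hours covered per day | Part of the night interval covered |
|---|---|---|
| 4 | 12 − 2 = 10 | 4/4 = 100% |
| 5 | 12 − 1 = 11 | 5/5 = 100% |
| 6 | 12 | 6/6 = 100% |
| 7 | 12 | 6/7 = 86% |
| 8 | 12 | 6/8 = 75% |
| 9 | 12 | 6/9 = 67% |
| 10 | 12 | 6/10 = 60% |

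Twelve hours is 12/24 = 50% of the day. The body text bars rescue SABA before home tests for 0 hours; it sets a 6-hour target for the timing of the test, which is a different thing.

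**The case against.** The case for leaving the cell alone has some force.

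- Section 3.8.1(f) is itself headed as a medication restriction and uses the same 6 hours. With tests fixed at waking and bedtime, the aim is close to the table's, and both texts use the word should. This narrows the gap but does not close it: feasibility is exactly what decides the matter when a patient needs rescue shortly before a fixed test.
- At clinic visits the consequence of a recent rescue dose is that the test waits or moves to another day, so the 6-hour wording need not mean refusing treatment. That procedure covers clinic visits only. Home tests have fixed times of day, and diary entries must be made within a set window (Section 5.3.2).
- The cell's first line separates routine use from use for symptoms, and its second permits nebulised rescue. Both soften the reading. Neither gives an exception to the 6-hour sentence, and metered-dose rescue is not mentioned in the cell.
- Nothing makes Appendix F override Section 3.8.1, no patient-facing instruction with the table's wording is shown, and harm would require staff to follow one cell while ignoring several sections. This stands, and it is why the point is minor.
- The hours per day rest on a literal reading and an assumed night interval. This also stands; they describe the wording and are not evidence of impact.

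**Conclusion.** The concern holds. As written, the SABA row of Table 5 contradicts Sections 3.8.1(f) and 5.1.3 on home testing, and it sits badly with the as-needed rescue permitted in 3.8.1(a) and 7.6.1.2. Its literal reach is 10 to 12 hours a day over assumed night intervals of 4 to 10 hours, and 60% to 100% of the night interval.

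The fault is confined to one cell, and the intended rule can be recovered from the rest of the protocol. Nothing shows that any rescue dose was withheld. Home PEF is not a key secondary endpoint, and no consequence for bias, power, type I error or the primary analysis is claimed. It should be corrected as a small matter of patient safety.

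**What to change.** Limit the 6-hour sentence in the SABA row of Table 5 to scheduled clinic spirometry and ECG. Then add to the same cell, in words such as: *Where feasible, time home PEF at least 6 hours after the last rescue dose of SABA. Rescue SABA for symptoms is always permitted and must not be withheld for the test.*

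This brings the table into line with rules already in the body. The cost is one table cell, with no new data, visits or patients.
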